5.2 Instructions for Discontinuation of Study Drug Administration for Safety Concerns

If, after appropriate consideration of study drug interruption/modification and consultation with the PTC Therapeutics medical monitor or designee, it is not appropriate for a subject to continue with study drug, then study drug should be permanently discontinued. If permanent discontinuation of study drug is the result of an SAE, then a follow-up SAE report form will be completed (see Section 8.5). In addition, details regarding the reasons for discontinuation and the AEs leading to the discontinuation should be recorded in the source documents and in the appropriate case report form (CRF). The EOS Visit CRF should be completed and appropriate follow-up (at ~4 weeks as per protocol or until recovery from or stabilization of the AE, whichever comes last) should be instituted.

Study drug may be permanently discontinued as a result of an SAE. If study drug is discontinued for lack of efficacy or other side effects, it will be reduced by 50% for 5 days and then discontinued.

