1.2.1 Ataluren

Ataluren (PTC124) is a novel 1,2,4-oxadiazole linked to 2 ring structures: fluorobenzene and benzoic acid. The molecule has no chiral centers. Its chemical name is 3-[5-(2-fluorophenyl)-1,2,4 oxadiazol-3-yl]-benzoic acid and its chemical formula is $C_{15}H_9FN_2O_3$. The compound has no structural similarity to other currently used drugs. The drug substance is a white to off-white, crystalline powder. The ataluren chemical structure is shown in Figure 1.

Figure 1 Ataluren Chemical Structure

Ataluren to be used in this study will be in the form of a white to off-white granules for suspension packaged in child-resistant aluminum foil packets. Each packet contains 125, 250, or 1000 mg of drug substance, which is 25% of the total formulation weight.

Ataluren is practically insoluble in water and has high permeability across layers of Caco-2 gastrointestinal epithelial cells. Ataluren, as well as its primary metabolite, an acyl glucuronide,

are excreted by both hepatic and renal routes. The plasma level peaks 1 to 2 hours after oral administration. The half-life ($t_{1/2}$) in healthy volunteers ranges from 2 to 6 hours. The side effects of ataluren that have been indicated in trials include vomiting, nausea, abdominal pain, headache, pyrexia, rhinitis, and sinusitis (PTC Therapeutics; ataluren Investigator's Brochure [IB]).

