1.5.1 Drug Administration Plan

Subjects will receive 12 weeks of ataluren or placebo during each treatment period. Treatment Period 1 will be followed by a 4-week Washout Period. Based on ataluren PK and pharmacodynamic data, the 4-week washout period is deemed an appropriate length of time to eliminate any ataluren drug effects. Following the Washout Period, subjects will crossover to receive the opposite treatment during Treatment Period 2 as follows:

- Subjects receiving ataluren during Treatment Period 1 will receive placebo during Treatment Period 2.
- Subjects receiving placebo during Treatment Period 1 will receive ataluren during Treatment Period 2.

Study drug will be administered 3 times per day (TID). The dose level to be administered is: 10 mg/kg in the morning, 10 mg/kg at midday, and 20 mg/kg in the evening.

Dosing will be based on the subject's body weight at Baseline. Weight will be assessed at every clinic visit. If the subject's body weight changes by $\geq 10\%$ from Baseline, the actual dose may be re-calculated.

The first dose of study drug will be administered in the clinic and the date and time of administration will be recorded. At the end of each Treatment Period, the last dose of study drug will be taken on the evening before the clinic visit (ie, the night before the Visit 4/Week 12 [end of Treatment Period 1] and the night before Visit 7/Week 28 [end of Treatment Period 2]).

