3.6 Early Withdrawal of Subjects

3.6.1 When and How to Withdraw Subjects

A subject may be discontinued from study drug at any time if the subject, subject's legal guardian, or the investigator feels that it is not in the subject's best interest to continue (see also Section 7). The following is a list of possible reasons for study drug discontinuation:

1. Parental/legal guardian withdrawal of consent.
2. Subject is not compliant with study procedures.
3. Protocol violation requiring discontinuation of study drug.
4. Severe adverse events, including significant toxicity such as severe cognitive or behavioral toxicity, impaired liver and renal function, or impaired hematopoiesis.
5. Seizure exacerbation not attributable to other known provocative factors.
6. Interaction with concomitant AED regimen that leads to unacceptable toxicity. Medication adjustments will be avoided, if possible, and may require the subject to exit the study, at the discretion of the Investigator.

Specific drug-related toxicities will be assessed and managed by the Principal Investigator.

Depending on the nature of the signs (eg, changes in serum chemistries, liver function tests) or symptoms (eg, rash), the subject will be assessed to determine the severity and likelihood of relation to study medication. Based on this assessment, the medication may be discontinued, the dose may be reduced, or the drug may be continued with ongoing assessment. If the study drug is discontinued due to a suspected toxicity, it will only be restarted if there is strong evidence that the toxicity was likely not related to the study medication (eg, liver tests were elevated due to a cytomegalovirus infection).

If a subject must discontinue study drug, the method for discontinuation from study drug will be determined based on the type of reaction and/or reason for withdrawal. For example, if the subject experiences a rapidly progressive rash, it would lead to abrupt cessation of study drug,

but if subject experiences excess tiredness, study drug may be tapered off. A discussion of the method of cessation will occur between the subject and/or subject's parent/legal guardian and the physician.

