If further evaluation reveals that the AE that led to dose interruption was not related to the study drug, study drug may be restarted.

If the subject experiences a recurrence of a previous abnormality that led to study drug dose interruption or experiences the new occurrence of an unacceptable AE or laboratory abnormality, the investigator will interrupt study drug and may confer with the appropriate personnel at PTC Therapeutics if needed regarding the potential need to discontinue study drug permanently.

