8.1.3 Serious Adverse Event

Adverse events are classified as serious or non-serious. A *serious adverse event* is any AE that is:

- fatal
- life-threatening
- requires or prolongs hospital stay
- results in persistent or significant disability or incapacity
- a congenital anomaly or birth defect
- an important medical event

Important medical events are those that may not be immediately life threatening, but are clearly of major clinical significance. They may jeopardize the subject, and may require intervention to prevent one of the other serious outcomes noted above. For example, study drug or other drug overdose or abuse, a seizure that did not result in inpatient hospitalization, or intensive treatment of bronchospasm in an emergency department would typically be considered serious.

Overdose of study drug is considered to be administration of a study drug dose > 4 times the intended total daily dose level for this protocol (> 160 mg/kg/day).

All AEs that do not meet any of the criteria for serious should be regarded as non-serious AEs.

Note that any SAEs occurring within 4 weeks of the date of last dose should be reported to the investigator who will notify PTC Therapeutics.

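### Section 5.2 prescribes a 5-day half-dose taper without exception, while Section 3.6.1 calls for abrupt cessation in a rapidly progressive rash; for a non-serious rash of that kind, a direct discontinuation cannot follow both

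*Combined protocol and SAP*

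**What the plan says.** Section 5.2 is the section on permanent discontinuation for safety concerns. It applies "after appropriate consideration of study drug interruption/modification and consultation with the PTC Therapeutics medical monitor or designee", once continuing is judged inappropriate. Its second paragraph first allows permanent discontinuation because of an SAE. It then says that drug "discontinued for lack of efficacy or other side effects, it will be reduced by 50% for 5 days and then discontinued". The wording is mandatory. No exception is given, nor any statement of which section prevails.

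Section 3.6.1 also covers how to stop. It makes the method depend on the reaction or the reason for withdrawal, and gives two examples. In the first, "if the subject experiences a rapidly progressive rash, it would lead to abrupt cessation of study drug". The second reads "but if subject experiences excess tiredness, study drug may be tapered off". The first is not conditioned on seriousness, and the second makes tapering optional. The same section allows drug stopped for suspected toxicity to be restarted only on strong evidence that the drug was probably not the cause.

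Section 5.1 leaves interruption for any adverse event to the investigator's judgment. Section 5.1.2 adds that if the subject "experiences the new occurrence of an unacceptable AE or laboratory abnormality, the investigator will interrupt study drug", and permits a restart when the event proves unrelated to study drug.

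**The concern.** Two sections tell the site how to stop the drug, and for one type of reaction they give opposite actions. A rapidly progressive rash is the protocol's own example of a reaction that needs an immediate stop. Yet 5.2, whose title is the one a site would look up when stopping for safety, prescribes five more days at half dose for any discontinuation that falls under its taper sentence.

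At stake is continued exposure of a child to a suspected cause of a progressing rash. Section 7.1 says enrolment has stopped, but the rule remains live: subjects in the open-label extension receive ataluren for 96 weeks (Table 1, footnote d), and Section 1.5 allows supply beyond Week 124.

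**Working it through.** The plan states no figure to reproduce. The check is a comparison of text, followed by simple arithmetic on the extra dose.

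**Which cases conflict**

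- *Rash classed as an SAE.* The taper sentence follows the SAE sentence and speaks of other side effects, so an SAE falls outside it. Section 3.6.1 governs. No conflict.
- *Excess tiredness.* Section 3.6.1 permits a taper and 5.2 requires one. Tapering satisfies both. The sections differ in force but do not contradict each other.
- *Rapidly progressive rash not classed as an SAE, discontinued directly.* Section 3.6.1 gives an abrupt stop; 5.2 gives half dose for 5 days. Both cannot be done.

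The third case can arise. Section 8.1.2 leaves seriousness to the investigator's judgment, and under 8.1.3 an event that meets no seriousness criterion is non-serious. Speed of progression is not itself a criterion. Nor does 5.2 require an interruption first; it requires only that one be considered.

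**Does interrupting first change the answer?** Yes. Once drug has been stopped for suspected toxicity, 3.6.1 bars a restart without strong evidence against a drug cause, and 5.1.2 ties a restart to the event being unrelated. Moreover, a 50% reduction presupposes a dose being taken; after an interruption there is none to reduce. The conflict is therefore confined to direct discontinuation.

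**Size of the difference**

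Inputs from the protocol: doses of 10, 10 and 20 mg/kg (Sections 1.5.1 and 4.2); 50% for 5 days (5.2); a half-life that "in healthy volunteers ranges from 2 to 6 hours" (1.2.1). Assumptions: body weights of 12, 20 and 40 kg, and a last half dose taken 108 to 120 hours after the decision to stop.

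- Full daily dose: 10 + 10 + 20 = 40 mg/kg.
- Half dose: 0.5 × 40 = 20 mg/kg/day.
- Extra dose under 5.2: 20 × 5 = 100 mg/kg, or 100 / 40 = 2.5 full-dose days. Under 3.6.1: 0.
- At the assumed weights: 100 × 12 = 1,200 mg; 100 × 20 = 2,000 mg; 100 × 40 = 4,000 mg.
- Five half-lives leave 0.5^5 = 3.1%. After an abrupt stop this takes 5 × 2 = 10 to 5 × 6 = 30 hours.
- With the taper: 108 + 10 = 118 to 120 + 30 = 150 hours after the decision.

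**Does the drug need a taper?** The protocol shows no general need. Section 1.5.1 says: "At the end of each Treatment Period, the last dose of study drug will be taken on the evening before the clinic visit". Section 6.1.1.4 dispenses no study drug at Week 12. Every subject completing Period 1 therefore stops from full dose without a taper, and 5.2 gives no reason for one.

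**The case against.** The strongest reply is that the protocol already leads a competent investigator to the right action. Section 3.6.1 names the reaction and the response, and a specific instruction would ordinarily override a general one. Section 5.2 pairs side effects with lack of efficacy, a non-urgent reason, so its sentence can be read as the schedule to use once a taper has been chosen. The investigator can interrupt at once. A rash severe enough to force withdrawal might also be classed as an important medical event, of which 8.1.3 says: "They may jeopardize the subject, and may require intervention to prevent one of the other serious outcomes noted above". That would take it outside the taper sentence.

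Much of this stands, and it keeps the point small. It does not remove the conflict. Nothing in the protocol says that 3.6.1 prevails, the wording of 5.2 is mandatory, and classification as an SAE is a judgment rather than a certainty. Stopping at once is the right action, but in this case it departs from the letter of 5.2.

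A reader might go further and infer that a permanent stop after an interruption obliges the site to resume half dose for 5 days. The documents do not support that, because the restart rules in 3.6.1 and 5.1.2 stand against it. A reader might also take 5.2 to speak expressly of non-serious side effects. It does not: the term is undefined, and that reading is inferred from the preceding SAE sentence. A broader reading would widen the conflict.

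**Conclusion.** Wrong as written, as a conflicting safety instruction, and of minor severity. The conflict is confined to direct discontinuation for a rapidly progressive rash that is not classed as an SAE. There, 5.2 read literally adds 100 mg/kg over 5 days where 3.6.1 adds none. This rests on reading other side effects as those other than SAEs. The milligram totals and the 118 to 150 hours also rest on the assumed weights and last-dose timing, and both time ranges use the healthy-volunteer half-life; these figures describe exposure, not harm.

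How often the case would arise cannot be estimated. The one rash reported as an event in the protocol is among those in three children under 6 years in an earlier study (Section 1.5.3); all of those events were mild or moderate, none was serious, and none led to discontinuation. Sample size, randomisation and the efficacy analysis are unaffected.

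**What to change.** Change Section 5.2 only, replacing the taper sentence with two:

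> If study drug is stopped for lack of efficacy, or for a side effect that does not call for abrupt cessation under Section 3.6.1, the dose may be halved for 5 days before stopping. Where the reaction calls for abrupt cessation (for example, a rapidly progressive rash), study drug is stopped without a taper, whether or not the event is an SAE.

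The word *may* also brings 5.2 into line with the optional taper for tiredness, and the reference to 3.6.1 settles which section decides the method. Section 3.6.1 needs no change. The cost is two sentences for one, with no new data, visits or procedures.

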6 SCHEDULE OF EVENTS AND STUDY PARAMETERS

6.1 Schedule of Events

The types and timing of data to be recorded are summarized in Table 1.

Table 1 Schedule of Events

Protocol Activities	Screening ^a	Treatment Period 1			4-Week Washout/ Crossover	Treatment Period 2 ^b		EOS Visit ^c or Begin Open- Label	Open-Label Extension ^d			End of Treatment	Follow Up ^e
		0	6	12		16	22		28	52	76		
Week (±6 days)	-4 (Wk -4 to Wk 0; Day -28 to Day 1)	0	6	12		16	22	28	52	76	100	124	128
Visit	1	2 ^f	3	4		5	6	7	8 ^g	9	10	11	12
Informed consent/assent	X												
Medical history	X												
Serum viral screen	X												
Physical examination	X	X		X		X		X	X	X	X	X	X
Height and weight	X	X	X	X		X	X	X	X	X	X	X	X
Vital signs	X	X	X	X		X	X	X	X	X	X	X	X
Seizure data diary provided	X	X	X	X		X	X	X	X	X	X	X	
Seizure data diary collected		X	X	X		X	X	X	X	X	X	X	X
Study drug dispensed		X ^h	X			X ^h	X	X ^h	X ^h	X ^h	X ^h		
Study drug administration		X ⁱ				X ⁱ		X ⁱ					
Study drug compliance and return			X	X			X	X	X	X	X	X	
Adverse events	X	X	X	X		X	X	X	X	X	X	X	X
Concomitant medications	X	X	X	X		X	X	X	X	X	X	X	X

Protocol Activities	Screening ^a	Treatment Period 1			4-Week Washout/ Crossover	Treatment Period 2 ^b		EOS Visit ^c or Begin Open- Label	Open- Label Extension ^d			End of Treatment	Follow Up ^e
		0	6	12		16	22		28	52	76		
Week (±6 days)	-4 (Wk -4 to Wk 0; Day -28 to Day 1)	0	6	12		16	22	28	52	76	100	124	128
Visit	1	2 ^f	3	4		5	6	7	8 ^g	9	10	11	12
Blood for CBC, CMP, LFTs, BUN, creatinine levels, serum HCG ^j	X	X		X		X		X	X	X	X	X	
Blood for plasma PK for ataluren ^k			X			X	X						
Blood for plasma PK for AED assessment ^l		X	X			X	X	X	X			X	
Urinalysis	X	X		X		X		X	X	X	X	X	
Behavior Assessment System for Children		X		X		X		X				X	
Vineland Adaptive Behavior Scales		X		X		X		X				X	
Quality of Life in Childhood Epilepsy		X		X		X		X				X	

Abbreviations: AED = antiepileptic drug; BUN = blood urea nitrogen; CBC = complete blood count; CMP = comprehensive metabolic panel; EOS = end of study; EOT = End of treatment; F/U = follow-up; HCG= human chorionic gonadotropin; LFTs = liver function tests; PK = pharmacokinetics; wk = week

a. Screening will occur from Week -4 to Week 0 (ie, 28 days). The ±6 day visit window is not applicable to the Screening Period.

b. During Treatment Period 2, subjects will crossover and begin receiving masked study drug opposite of what they received during Treatment Period 1 (ie, subjects previously receiving masked ataluren will now receive placebo and subjects previously receiving placebo will now receive ataluren).

01 Aug 2019

- c. The EOS visit (Week 28) will be completed for all subjects who complete or discontinue early from Treatment Period 1 and 2. Subjects who complete the EOS visit may continue in the open-label portion of the study at Week 28, otherwise a follow-up visit should be scheduled after 4 weeks.
- d. All subjects enrolling in the open-label extension study will receive ataluren 10, 10, 20 mg/kg 3 times per day for 96 weeks.
- e. The Follow-up visit is to occur 4 weeks after the last dose of study drug, regardless of whether the subject discontinues prematurely or completes the EOS visit and/or the open-label extension.
- f. Visit 2 is considered the Baseline Visit. Visit 2 must occur no sooner than 28 days and up to 42 days after Visit 1. All study and laboratory assessments must be completed prior to the first dose of study drug administration.
- g. If the subject begins but does not complete the open-label extension, complete EOT (Week 124).
- h. The first dose of study drug should be given in the clinic at Visit 2 (Baseline), Visit 5 (Week 16), and, if applicable, in the open-label extension at Visit 7 (Week 28).
- i. The last dose of study drug prior to Visit 4/Week 12 (Treatment Period 1) and Visit 7/Week 28 (EOS Visit) should be taken the night before, at home. No morning dose should be taken prior to the clinic visit.
- j. Serum HCG samples taken only for female subjects of childbearing potential
- k. Ataluren plasma PK will be assessed at 0 hr (pre-dose) at Visit 5/Week 16 and at 0 hr (pre-dose) and 2 hr post-dose at Visit 3/Week 6 and Visit 6/Week 22.
- l. AED plasma PK will be assessed at 0 hr (pre-dose of AED, including but not limited to valproate, clonazepam, lamotrigine, topiramate, and levetiracetam).

6.1.1 Screening, Treatment, and Follow-up Periods

The investigator/study staff member must inform each study candidate or parent/legal guardian of the nature of the study, explain the potential risks, and obtain written informed consent/assent from the study candidate and/or parent(s)/legal guardian (as required by local regulations) prior to performing any study-related Screening procedures. Screening evaluations for the study will be performed at the clinical research facility. Study participants will report to the clinic on the morning of each scheduled on-site visit and will remain in the clinic until released by the investigator after all study-related procedures have been completed and the subject has been instructed regarding drug storage, reconstitution, and administration.

Adverse events will be assessed beginning at the time of informed consent through the end of the follow-up period.

Subjects must return to the clinic for a follow-up assessment at 4 weeks after the last dose. If subjects enroll in the open-label extension, follow-up assessment will occur 4 weeks after the last dose of the extension period.

6.1.1.1 Visit 1 (Screening, 4 Weeks Prior to Baseline Visit 2)

The Screening Visit (Visit 1) will occur 4 weeks prior to the Baseline Visit during a routine visit at NYU CEC. Screening procedures will proceed as follows:

- Obtain written informed consent/assent.
- Determine if the subject meets the preliminary eligibility criteria:
 - Collect demographic information
 - Collect current and relevant medical history
 - Identify concomitant medications used
 - Identify and confirm stable use AED medications

If the subject meets the preliminary eligibility criteria, the following assessments will be performed:

- Vital signs (including systolic and diastolic blood pressure, radial pulse rate, and body temperature): perform in sitting position
- Physical examination
- Height and weight
- Blood draw for clinical laboratory evaluations:
 - Blood urea nitrogen (BUN), complete blood count (CBC), comprehensive metabolic panel (CMP), liver function tests (LFTs) and creatinine levels
 - Serum human chorionic gonadotropin (HCG), as applicable (sample taken only for female subjects of childbearing potential)
 - Serum viral screen
- Urinalysis
- Record any AEs occurring since signing the ICF and any that occur during this visit

- Instruct subject or subject's caregiver to keep a seizure diary for the next 4 weeks, including the following information:
 - Seizure type, duration, intensity
 - Presence or absence of cyanosis
 - Use of rescue medications

6.1.1.2 Visit 2 (Baseline, Week 0)

After the 4-week Screening period, the diary card provided at the Screening Visit will be reviewed and all inclusion/exclusion criteria will be confirmed. Eligible subjects complete the Baseline Visit (Visit 2/Week 0) as follows:

- Physical examination
- Height and weight
- Vital signs (including systolic and diastolic blood pressure, radial pulse rate, and body temperature): performed after the subject has been in a sitting position for 3–5 minutes
- Collect seizure diary and review entries
- Record any AEs occurring since last visit and any that occur during this visit
- Record any changes in concomitant medications
- Complete the following QOL assessments:
 - Behavior Assessment System for Children
 - VABS-II
 - QOLCE
- Blood draw for clinical laboratory evaluations
 - CBC, CMP, LFTs, BUN, creatinine, serum HCG
 - Plasma PK for AED level assessment (0 hr, pre-dose)
- Urinalysis
- Dispense new seizure diary and review instructions for completion
- Dispense masked study drug and review administration instructions
 - TID dosing 10 mg/kg, 10 mg/kg, 20 mg/kg (morning, midday, evening)
 - The first dose of study drug should be administered in the clinic *after* completion of all other assessments and procedures required at this visit.
- Instruct subject to return in 6 weeks for Visit 3

